CTCAE	Common Terminology Criteria for Adverse Events
CSF-1	Colony Stimulating Factor 1
CSF-1R	Colony Stimulating Factor 1 Receptor
DILI	drug-induced liver injury
DLRM	Dose Level Review Meeting
DLRT	Dose Level Review Team
DLT	dose limiting toxicity
dMMR	deficit in mismatch repair genes
DOR	duration of response
ECG	electrocardiogram
ECOG	Eastern Cooperative Oncology Group
EDC	electronic data capture
End of Study for Individual Subject	defined as the last day that protocol-specified procedures are conducted for an individual subject (ie, the date the subject withdraws full consent from the study, completes the safety follow-up visit or long-term follow-up [whichever is later] or death).
End of Study (primary completion)	defined as when the last subject is assessed or receives an intervention for the purposes of final collection of data for the primary endpoint(s).
End of Study (end of trial)	defined as when the last subject is assessed or receives an intervention for evaluation in the study; if the study includes multiple parts (eg, safety follow-up or survival assessment), the end of study would include these additional parts
End of Treatment	defined as the last assessment for the protocol-specified treatment phase of the study for an individual subject
Heart rate	number of cardiac cycles per unit of time
HIV	human immunodeficiency virus
IB	Investigator's Brochure
ICF	informed consent form
ICH	International Conference on Harmonisation

Abbreviation or Term	Definition/Explanation
IL	interleukin
ILD	interstitial lung disease
INR	international normalization ratio
IPIM	Investigational Product Instruction Manual
IRB/IEC	institutional review board/independent ethics committee
irCR	Immune-related complete response
irPR	Immune-related partial response
irRECIST	Immune-related Response Evaluation Criteria in Solid Tumors (RECIST)
irSD	Immune-related stable disease
irPD	Immune-related progressive disease
IV	intravenous
LDH	lactate dehydrogenase
MRI	magnetic resonance imaging
NSCLC	non-small cell lung cancer
OR	objective response
ORR	objective response rate
OS	overall survival
PD	progressive disease
PD-1	programmed cell death-1
PD-L1	programmed death ligand 1
PET	positron emission tomography
PFS	progression free survival
PK	pharmacokinetics
PR	partial response
PR Interval	PR interval is measured from the beginning of the P wave to the beginning of the QRS complex in the heart's electrical cycle as measured by ECG
PT	prothrombin time

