6.2.1.2.3 Dose-limiting Toxicity Definition

An adverse event will be considered related to study treatment (possibly, probably, or definitely related to the study treatment) if there is a suspected “reasonable causal relationship” to the study treatment (ICH E2A), and not only a lack of an alternative explanation for the toxicity. All toxicities will be graded using the CTCAE version 4.0 ([Appendix A](#)).

The occurrence of any of the following toxicities during DLT evaluation period (ie, 21 day period from the initial administration of AMG 820 and pembrolizumab in combination) will be considered a DLT, if judged by the investigator to be related to the administration of AMG 820 and/or pembrolizumab:

- Grade 4 non-hematologic toxicity
- Grade 3 or higher pneumonitis
- Grade 3 non-hematologic toxicity lasting > 7 days despite appropriate treatment
 - Grade 3 fatigue will not be classified as DLT, irrespective of duration
- Any grade 3 or higher non-hematologic laboratory value if:
 - medical intervention is required, or
 - the abnormality leads to hospitalization, or
 - the abnormality persists at grade 3 or higher for >1 week unless deemed not clinically important per both investigator and sponsor
- Grade 3 or grade 4 febrile neutropenia

- Grade 3 or higher thrombocytopenia with bleeding and Grade 4 or higher thrombocytopenia lasting > 48 hours or any thrombocytopenia requiring intervention
- Delay in cycle 2 treatment for > 2 weeks due to study drug-related toxicity (unless clearly attributable to pembrolizumab only and delay is caused due to tapering of steroids)
- Any other intolerable toxicity leading to permanent discontinuation of AMG 820 or pembrolizumab

Lymphopenia of any grade is not considered a DLT

Dose limiting toxicities do not include the following:

- A transient (resolving to grade ≤ 1 within 6 hours of onset) grade 3 infusion-related adverse event
- Any grade 3 endocrinopathy that is adequately controlled by hormonal replacement

Cumulative adverse events profile will be taken into consideration when making decisions on dose escalation or de-escalation.

If an AE is clearly attributable to pembrolizumab (based on its known safety profile) and does not exceed the expected severity, this specific AE may be considered exempt from being a DLT.

Disease related events should not be considered a DLT.

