6.2.3 Management of AMG 820 Related Periorbital or Conjunctival Swelling

If a subject experiences grade 3 (severe) periorbital or conjunctival swelling, the study treatment should be withheld until the toxicity resolves or improves to grade 2 (moderate). If the event requires > 4 weeks to recover to grade 2 or lower (with or

without appropriate therapeutic intervention), the subject will be discontinued from the study and should be followed until the swelling resolves to grade 2. Appropriate therapeutic intervention (eg topical 1% hydrocortisone with 0.25% phenylephrine and/or diuretics) to resolve the swelling may be administered at the discretion of the Investigator to any subject experiencing periorbital edema or conjunctival swelling of any grade.

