7.2.3 Safety Follow-up Visit(s)

All subjects will complete a safety follow-up visit approximately 135 (+7) days after the last dose of study treatment.

The following procedures will be performed:

- Physical examination as per standard of care including ECOG performance status assessment. Physical examination findings should be recorded on the appropriate CRF (eg, medical history, event)
- Body weight in kilograms should be measured without shoes.
- Vital signs (systolic/diastolic blood pressure, heart rate, respiratory rate, temperature): Subject should be in a supine position in a rested and calm state for at least 5 minutes before blood pressure assessments are conducted. If the subject is unable to be in the supine position, the subject should be in most recumbent position as possible. The position selected and temperature location for a subject should be the same that is used throughout the study and documented on the vital sign CRF. Record all measurements on the vital signs CRF
- A 12-lead ECG per standard of care: The ECG must include the following measurements: heart rate, PR, QRS, QT and QTc intervals. Subject must be in supine position in a rested and calm state for at least 5 minutes before ECG assessment is conducted. If the subject is unable to be in the supine position, the subject should be in most recumbent position as possible. The investigator or designated site physician will review all ECGs. Once signed, the original ECG tracing will be retained with the subject's source documents. At the request of the sponsor, a copy of the original ECG will be made available to the Sponsor.
- Local laboratory Assessments
 - hematology panel
 - chemistry panel
 - lipase and amylase
 - coagulation: PT or INR and PTT or a PTT
 - thyroid function tests: T3 (or FT3), FT4, TSH
 - urinalysis
 - serum or urine pregnancy test for female subjects of childbearing potential

- Central laboratory assessments (refer to Schedule of Assessments as not all tests will be required after Amendment 2):
 - All subjects
 - Blood for immunogenicity
- Radiographic tumor imaging and tumor response assessments are to be performed if the subject ended study treatment prior to confirmed PD per irRECIST and has not had assessments performed within 6 weeks of the visit.

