7.2.4 Long-term Follow-up

After the safety follow-up visit all subjects will enter the long-term follow-up. Subjects will be contacted by clinic visit or telephone to assess survival, disease status and initiation of first subsequent anti-tumor therapy following end of AMG 820 and pembrolizumab treatment.

Contact for all subjects will be attempted every 12 weeks (\pm 28 days) following the safety follow-up visit, as applicable, until death, subject withdraws full consent, or up to 12 months after subject's enrollment for the study, whichever comes first.

For subjects who discontinued treatment for any reason other than confirmed PD, every effort should be made to perform radiographic imaging (CT or MRI) of the chest, abdomen and pelvis, along with tumor assessments of all other sites of disease every 12 weeks until documentation of confirmed PD per irRECIST, clinical progression, start of new anticancer therapy, or up to 12 months after subject's enrollment for the study, whichever occurs first.

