8.3 Reasons for Removal From Treatment, or Study

8.3.1 Reasons for Removal From Treatment

Reasons for removal from protocol-required investigational product(s) or procedural assessments include any of the following:

- subject request
- safety concern (eg, due to an adverse event, ineligibility determined, protocol deviation, non-compliance, requirement for alternative therapy)
- pregnancy
- potential hepatotoxicity (as per [Section 6.4.1](#))
- other protocol-specified criteria (see [Sections 6](#))
- death
- lost to follow-up
- decision by Sponsor (other than subject request, safety concern, lost to follow-up)
- disease progression

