8.3.2 Reasons for Removal From Study

Reasons for removal of a subject from the study are:

- decision by sponsor
- withdrawal of consent from study
- death
- lost to follow-up

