#### Investigational Product

The term 'investigational product' is used in to reference to AMG 820 in combination with pembrolizumab.

---

Last Investigational Product Dose Date

The last AMG 820 dose date for each subject is defined as the latest date AMG 820 is administered.

Objective Response as per irRECIST (irOR)

Objective response is defined as a complete response or partial response, as defined by the irRECIST. Confirmation is done by a repeat, consecutive assessment no less than 4 weeks from the date of first documented assessment.

Objective Response Rate as per irRECIST (irORR)

Immune-related ORR (irORR) is defined as the percentage of subjects with irOR.

Overall Survival Time

Overall survival time is calculated as the number of days from the first administration of AMG 820 to death or if applicable censoring [(date of death or censoring – date of first dose of AMG 820 + 1)]. Subjects who withdraw from treatment without withdrawing consent will be followed for survival status up to 12 months.

Subjects who are alive (no record of death) and are lost to follow-up will be censored at the date of last contact.

Progression-Free Survival Time per irRECIST (PFS)

Progression-free survival time is calculated as the number of days from the first administration of AMG 820 to the first assessment of disease progression as per irRECIST or death due to any cause, or if applicable date of censoring (date of progressive disease or death or censoring – first administration of AMG 820 +1).

The following censoring strategies will be used for the progression free survival analysis:

If a subject's disease has not progressed and the subject is alive, progression-free survival time will be censored at the last date they are known to be progression-free (ie, the last evaluable radiological assessment date).

If a subject has no tumor evaluation in the study, progression-free survival time will be censored at the date of the first administration of AMG 820.

Subjects who withdraw consent to participate in the study prior to disease progression will be censored at their last evaluable radiological assessment date.

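### Section 6.2.3 takes a subject with prolonged grade 3 eye swelling off the study, where the rest of the protocol takes such a subject off treatment and keeps following

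*Protocol*

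**What the plan says.** Under Protocol Section 6.2.3, study treatment is withheld for grade 3 swelling until it improves to grade 2. If that takes more than 4 weeks, "the subject will be discontinued from the study and should be followed until the swelling resolves to grade 2". No other follow-up is named.

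Elsewhere the documents separate stopping treatment from leaving the study:

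- **Section 8.3.1** covers removal from investigational product or procedural assessments. Its list includes "safety concern (eg, due to an adverse event, ineligibility determined, protocol deviation, non-compliance, requirement for alternative therapy" and also the criteria set out in Section 6.
- **Section 8.3.2** opens "Reasons for removal of a subject from the study are" and gives four items: sponsor decision, withdrawal of consent from the study, death and loss to follow-up.
- **Study Glossary** ends an individual's study at "the date the subject withdraws full consent from the study, completes the safety follow-up visit or long-term follow-up [whichever is later] or death".
- **Section 7.2.3**: "All subjects will complete a safety follow-up visit approximately 135 (+7) days after the last dose of study treatment".
- **Section 7.2.4** sends all subjects into long-term follow-up and adds: "For subjects who discontinued treatment for any reason other than confirmed PD, every effort should be made to perform radiographic imaging".
- **Section 9.2.2.1** requires adverse event reporting through the 135 (+7) day safety visit.
- **SAP Section 6, Overall Survival Time**: "Subjects who withdraw from treatment without withdrawing consent will be followed for survival status up to 12 months".

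**The concern.** Section 6.2.3 is mandatory, specific to one toxicity, and phrased at the level of the study. A site holding it alongside the general follow-up rules has two instructions that cannot both be carried out. If the site follows 6.2.3, the subject could be closed out once the swelling reaches grade 2.

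The data at stake are adverse events up to 135 (+7) days after the last dose, treatment-related serious adverse events reported through long-term follow-up (Section 9.2.2.2), post-treatment tumor assessments, and the survival contacts that feed PFS and OS at 6 and 12 months. Treatment-emergent adverse events are a primary endpoint, and the SAP counts them over the same 135 (+7) days. The loss would also be tied to a drug effect: Sections 2.2.1 and 2.3 name periorbital edema among the common AMG 820 toxicities.

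**Working it through.** This is a check of wording, and the plan gives no figure to reproduce.

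**1. Where the event belongs.** Section 6.2.3 is itself a Section 6 criterion, and the event is an adverse event. Section 8.3.1 places both under removal from treatment or procedural assessments. None of the four items in 8.3.2 is toxicity. Sponsor decision is on that list, and Section 8.2 lets the investigator or sponsor withdraw a subject from the whole study, but both routes are discretionary. Section 6.2.3 makes removal automatic.

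**2. The general rule for the same event.** The dose-limiting toxicity definition in 6.2.1.2.3 includes "Grade 3 non-hematologic toxicity lasting > 7 days despite appropriate treatment" when related to study drug. Related grade 3 swelling lasting over 4 weeks despite treatment meets it. For such an event after day 21, 6.2.1.2.3 calls for therapy to stop. It does not end study participation.

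**3. Internal sense of 6.2.3.** The sentence before the quoted one is about withholding study treatment, and the quoted sentence itself asks for further follow-up. Both point to treatment discontinuation as the intent.

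**4. Long-term follow-up.** Section 3.5.1 says that only some subjects enter it, depending on treatment duration. That fits the limit in 7.2.4 of 12 months from enrollment. The safety visit falls before day 365 if the last dose is before about day 365 − 135 = 230, or 365 − 142 = 223 with the +7 window. A subject stopped early for toxicity is therefore one who would enter long-term follow-up.

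**5. Illustration of the adverse event gap.** This is one hypothetical subject under the literal reading, not an estimate. Assumptions: the 4 weeks run from grade 3 onset; swelling reaches grade 2 just after 4 weeks, so close-out is 29 days after onset; dosing is every 21 ± 3 days with no delays, so onset is 0 to 24 days after the last dose.

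- Close-out: 29 + 0 = 29 to 29 + 24 = 53 days after the last dose.
- Part of the 135-day window not covered: 135 − 53 = 82 to 135 − 29 = 106 days.

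Longer swelling or a dose delay before onset shortens the gap.

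**6. Can PFS or TTP be censored at first dose?** The SAP does this only when there is no tumor evaluation. Section 7.4 calls for a scan at end of study or end of treatment if the last one was at least 6 weeks earlier and progression is not confirmed. Take onset on day d, close-out on day d + 29 (treated as end of treatment), and a screening scan k days before day 1 as the only scan. The gap is d + 28 + k days, which reaches 42 when d + k ≥ 14. No scan is called for only if d + k ≤ 13, so first-dose censoring would need very early onset and a recent screening scan.

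**The case against.** The strongest reply is that the protocol already settles the matter. Section 8.3.1 sends Section 6 criteria to treatment removal; 7.2.3 and 7.2.4 apply to all subjects; and 6.2.3 cannot mean complete removal because it asks for continued follow-up. Section 6.2.1.3 is equally loose: it calls for end-of-study procedures in subjects withdrawn from therapy, and for a dose-limiting toxicity it names only follow-up of the event. Study removal is also not forbidden, given 8.2 and the sponsor-decision item. Finally, Amendment 2 records that the sponsor has decided to stop investigating the combination, which limits future exposure.

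Much of this stands. It establishes the intent and keeps the point minor. It does not remove a mandatory instruction that contradicts the follow-up rules. The loose wording in 6.2.1.3 makes early close-out an easier misreading, and discretionary routes do not justify automatic removal.

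A reader might also infer that the Section 7.4 scan always protects the imaging data once onset is day 14 or later. It does not. With onset on day 60, a week-10 scan on day 64 and close-out on day 89, the last scan is 25 days old and no further scan is called for. That subject has a tumor evaluation, so first-dose censoring does not arise, but later assessments could still be missed.

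**Conclusion.** The conflict is real and minor. Section 6.2.3 ends study participation for a toxicity that the rest of the protocol and the SAP treat as a reason to stop treatment and keep following. The consequence is conditional on a site preferring 6.2.3 over the all-subject rules.

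The number affected is unknown and probably very small. No section reports grade 3 swelling lasting over 4 weeks, and a related case would usually already have met the treatment-stopping rule in 6.2.1.2.3. The 82 to 106 day gap holds only under the assumptions stated with it.

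A reader might infer a loss of power or a biased response rate. The documents do not support either. Efficacy is analyzed on all enrolled subjects with at least one dose of AMG 820, so the denominator is unchanged, and nothing gives a frequency from which to claim an effect. Nor do the documents support saying that data have been or will be lost, because the sections requiring the follow-up remain in force.

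**What to change.** In Section 6.2.3, replace the words that take the subject off the study with *permanently discontinued from study treatment*. Add one sentence: *Tumor assessments, the 135-day safety visit and long-term follow-up continue per Sections 7.2.3, 7.2.4 and Table 5.*

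Amendment 2 made the same correction to the pregnancy rule in 6.2.4.10.3, which now removes the subject from study treatment. For consistency, the end-of-study procedures in 6.2.1.3 could be read, or reworded, as end-of-treatment procedures.

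The cost is a few words and one sentence. No withholding or stopping threshold changes, no visit or scan is added, and the option in 6.2.1.3 to continue the other drug alone is left as it is.

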6.2.4 Rescue Medications and Supportive Care Guidelines for Pembrolizumab

Subjects should receive appropriate supportive care measures as deemed necessary by the treating investigator including, but not limited to, the items outlined below. If a subject requires corticosteroid dosing of > 10 mg prednisone daily (or equivalent) as supportive care, AMG 820 and pembrolizumab dosing must be withheld until the corticosteroid dose has decreased to ≤10 mg prednisone daily (or equivalent) as detailed in [Section 6.2.2.2](#).

6.2.4.1 Pneumonitis and Interstitial Lung Disease (ILD)

Subjects with symptomatic pneumonitis, ILD, or acute interstitial pneumonitis (symptoms may include but are not limited to abnormal breath sounds, chest pain and/or tightness, dyspnea, dry cough, fatigue, fever, hemoptysis) should immediately stop receiving pembrolizumab and have an evaluation. The evaluation may include bronchoscopy and pulmonary function tests to rule out other causes such as infection. All attempts should be made to rule out other causes such as metastatic disease, bacterial or viral infection. It is important that subjects with a suspected diagnosis of pneumonitis be managed as per the guidance in [Table 3](#). until treatment-related pneumonitis is excluded. Treatment of both a potential infectious etiology and pneumonitis in parallel may be warranted. Management of the treatment of suspected pneumonitis with steroid treatment should not be delayed for a therapeutic trial of antibiotics. If an alternative diagnosis is established, the subject does not require management as in [Table 3](#); however, the adverse event should be reported regardless of etiology.

If the subject is determined to have pembrolizumab associated pneumonitis, ILD, or acute interstitial pneumonitis, the suggested treatment is as follows (detailed plan in [Table 3](#)).

- For grade 2 events, treat with systemic corticosteroids. When symptoms improve to grade 1 or less, steroid taper should be started and continued over no less than 4 weeks.
- For grade 3-4 events, immediately treat with intravenous steroids. Administer additional anti-inflammatory measures, as needed.
- Add prophylactic antibiotics for opportunistic infections in the case of prolonged steroid administration.

Table 3. Recommended Approach to Handling Pneumonitis and ILD

Pembrolizumab Drug Associated Pneumonitis and ILD	Withhold/Discontinue Pembrolizumab?	Supportive Care
Grade 1 (asymptomatic)	No action	Intervention not indicated.
Grade 2	Withhold pembrolizumab, may return to treatment if improves to grade 1 or resolves within 12 weeks	
Consider pulmonary consultation with bronchoscopy and biopsy/ bronchoalveolar lavage (BAL) and infectious disease consultation if appropriate.
 
Conduct an in person evaluation approximately twice per week until the subject is improving. Consider frequent Chest X-ray as part of monitoring.
 
Treat with systemic corticosteroids at a dose of 1 to 2 mg/kg/day prednisone or equivalent. When symptoms improve to grade 1 or less, steroid taper should be started and continued over no less than 4 weeks. Permanently discontinue for inability to reduce corticosteroid dose to 10 mg or less of prednisone or equivalent per day within 12 weeks.
 
Discontinue pembrolizumab if upon re-challenge the subject develops a second episode of grade 2 or higher pneumonitis.

Recurrent Grade 2 Grade 3 and Grade 4	Discontinue pembrolizumab Discontinue pembrolizumab	
Supportive care per instructions for Grade 2 above.
 
Hospitalize the subject and consider bronchoscopy with biopsy and/or BAL. Immediately treat with intravenous steroids (methylprednisolone 125 mg IV). When symptoms improve to Grade 1 or less, a high dose oral steroid (prednisone 1 to 2 mg/kg once per day or dexamethasone 4 mg every 4 hours) taper should be started and continued over no less than 4 weeks. If IV steroids followed by high dose oral steroids does not reduce initial symptoms within 48 to 72 hours, treat with additional anti-inflammatory measures. Discontinue additional anti-inflammatory measures upon symptom relief and initiate a prolonged steroid taper over 45 to 60 days. If symptoms worsen during steroid reduction, initiate a re-tapering of steroids starting at a higher dose of 80 or 100 mg followed by a more prolonged taper and administer additional anti-inflammatory measures, as needed. In addition, prophylactic antibiotics for opportunistic infections should be considered.

IV = intravenous

